ORGANIZATION OF DETAILED PROTOCOL

Title: Boston-Harvard Burn Injury Model System: Cortical modulation with transcranial direct current stimulation (tDCS) for neuropathic symptoms following burn injury.

Protocol #: 2012-p-001996

Date: 03/21/2016

[REDACTED]

[figure not shown]
[REDACTED]

[REDACTED]

[REDACTED]

[REDACTED]

Dysfunction of Neural Pathways in Burn

[REDACTED]

[REDACTED]

[REDACTED]

[REDACTED]

[REDACTED]

[figure not shown]

II. SPECIFIC AIMS

The overall goal for this project is to develop a novel treatment using transcranial direct current stimulation (tDCS) for patients with neuropathic burn symptoms such as pain or itching. Because the interventions to date for this group of patients (mainly drugs) have been marked by limited clinical effectiveness [14], the results of this study will represent an initial, significant step toward providing a new therapeutic alternative to this group of patients. Finally we will also collect neurophysiological data to understand further the mechanistic effects of this novel intervention and compare with the use of tDCS for other chronic pain syndromes.

The following aims will be explored in this study:

Aim 1 - To assess the effects of tDCS treatment on neuropathic symptoms: pain or itching – following burn injury. We will determine the magnitude of pain reduction with the modified Brief Pain Inventory (BPI) and itch severity/activity with the Visual Analog Scale (VAS) and 5-D Scales in active tDCS compared with sham tDCS. *Our first hypothesis is that active tDCS will be associated with a larger pain or itching reduction assessed by BPI and Itch VAS/5-D.*

IV. SUBJECT SELECTION

We will select 60 subjects that have burn injury and meet the following criteria:

Inclusion Criteria:

1. Providing informed consent to participate in the study
2. Age 18 or older
3. Burn injury with pain and/or itch that is moderate to severe (at least 4 on the visual analogue scale during the previous 3 weeks)
4. Burn injury occurred at least 3 weeks prior to enrollment. Patient must be discharged from acute inpatient care. (Patient can be enrolled in either inpatient rehabilitation and/or outpatient care)

Exclusion Criteria:

1. Subjects with burns in scalp in the area of electrode placement (i.e. within 4 cm of the DLPFC and the reference site) as the electrode may cause irritation to the injuries
2. Psychiatric disorders that have led to hospitalization within the past 6 months or signs of suicidality

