Primary and Secondary Employment Status: As part of the vocational sub-aim of this study, we will assess the employment status, and in particular the intention to seek employment, of each subject. Codes include: unemployed, unemployed but searching for work, part time or full time student, employed, or retired. These are the same employment rating scale codes used already in the model systems database.

Sleep Assessments: We will measure sleep outcomes using the Pittsburgh Sleep Quality Index, Insomnia Severity Scale, and VAS for sleep. We will also have the subjects keep a very short diary looking at sleep for the first 4 weeks of the study.

Medication Use Questionnaire and Diary: We will obtain a medication use history at study entry using a standardized questionnaire similar to that used in our prior tDCS studies, and update this information at each subsequent visit. We will also monitor patient medication throughout the course of the study using a subject Medication Diary. Participants will be required to record medications daily in a pain medication diary. Participants will be instructed to keep the pain medication diary throughout the baseline, treatment, and follow-up period. This diary will be maintained until completion of the study.

[figure not shown]

VII. STATISTICAL ANALYSIS

As study outcomes will be measured at baseline and several timepoints up to 12 months (post-enrollment), continuous and categorical outcomes will be analyzed by methods of longitudinal analysis using generalized estimating equations with an unrestricted covariance matrix, to estimate model parameters and test hypotheses. Tests of equality of the change from baseline to 12 months in the two treatment groups will be based on the estimate of the time (12 months versus baseline) by treatment interaction. This will allow participants who are seen at some follow-up visits but not at 12 months to contribute to the analysis. Time to event variables such as time to return-to-work will be analyzed by proportional hazards regression and Kaplan Meier estimation of time to event distributions.

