Midway through the study, a power analysis will be performed to reassess the sample size needed to successfully complete this project. In this analysis, we will only look at the variability parameters (variance) and compare it to the one estimated before the study. We will not look at the effect estimates and therefore do not anticipate Type I error increase. This power analysis will be performed by a staff member (Co-Investigator) not involved with the analysis and conduct of the study. All blinded staff members will remain blinded.

The primary endpoint for this study is pain intensity as measured by the BPI. The study will have three secondary endpoints: itch as measured by the VAS scale, depression as measured by BDI and neural activity changes measured by somatosensory ERPs. These secondary outcomes represent three domains in which tDCS are anticipated to be effective. The same analytic approach will be employed in the analysis of the primary and secondary outcomes. For the outcomes, exploratory univariate analysis comparing active vs. placebo tDCS will be conducted. If a significant treatment effect is detected, similar adjusted longitudinal regression analysis will be performed; however these analyses will be considered hypothesis generating a p values interpreted cautiously given the increased likelihood of a false positive result given the false positive problem.

[REDACTED]

[REDACTED]

[REDACTED]

[REDACTED]

[REDACTED]

[REDACTED]

[REDACTED]

[REDACTED]

[REDACTED]

[REDACTED]

[REDACTED]

[REDACTED]

[REDACTED]

[Redacted]

[Redacted]

[Redacted]

[Redacted]

[Redacted]

[Redacted]

[Redacted]

[Redacted]

[Redacted]

[Redacted]

[Redacted]

[REDACTED]

[REDACTED]

[REDACTED]

[REDACTED]

[REDACTED]

[REDACTED]

[REDACTED]

XI. REFERENCES

2. Schneider, J.C., et al., *A descriptive review of neuropathic-like pain after burn injury*. J Burn Care Res, 2006. 27(4): p. 524-8.
3. Holavanahalli, R.K., P.A. Helm, and K.J. Kowalske, *Long-term outcomes in patients surviving large burns: the skin*. J Burn Care Res, 2010. 31(4): p. 631-9.
4. Malenfant, A., et al., *Prevalence and characteristics of chronic sensory problems in burn patients*. Pain, 1996. 67(2-3): p. 493-500.

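### The adjusted longitudinal regression is run only after a significant effect, so the adjusted estimates are selected on significance; the primary BPI analysis is not labelled in the visible text

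*Combined protocol and SAP*

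**What the plan says.** Everything relevant is in the combined protocol and SAP, VII. Statistical Analysis, with the hypothesis in II. Specific Aims.

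- **First paragraph of Section VII.** Continuous and categorical outcomes are analysed by "longitudinal analysis using generalized estimating equations with an unrestricted covariance matrix, to estimate model parameters and test hypotheses". Tests of change from baseline to 12 months "will be based on the estimate of the time (12 months versus baseline) by treatment interaction". No condition is attached. The paragraph does not mention BPI and does not call this test primary.
- **Paragraph on endpoints, later in Section VII.** "The primary endpoint for this study is pain intensity as measured by the BPI". Itch VAS, BDI and somatosensory ERPs are secondary. Then: "The same analytic approach will be employed in the analysis of the primary and secondary outcomes".
- **Next sentences of that paragraph.** The first adds a univariate step: "For the outcomes, exploratory univariate analysis comparing active vs. placebo tDCS will be conducted". The second makes a further model depend on the result: "If a significant treatment effect is detected, similar adjusted longitudinal regression analysis will be performed". A closing clause sets the status of this work: "however these analyses will be considered hypothesis generating". It adds that the p values need caution because of false positives.
- **Aim 1.** The hypothesis is that "active tDCS will be associated with a larger pain or itching reduction assessed by BPI and Itch VAS/5-D". It covers pain or itching, so it is the endpoint sentence in Section VII that singles out BPI.

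Redacted blocks follow the endpoint paragraph. What is said here about silence concerns the visible text only.

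**The concern.** The conditional sentence is an explicit rule, and it makes the existence of an estimate depend on its being favourable. A trial that misses significance reports no adjusted longitudinal effect. A trial that reaches it reports an adjusted effect from a subset of possible results in which chance has, on average, helped. Anyone who later uses the adjusted estimate for planning or pooling would start from a number that is too large, or have none.

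The second part is a matter of labelling. The sentence on exploratory comparisons follows directly on the sentence about primary and secondary outcomes and excludes none of them. The text does not say which test supplies the significant effect, or how this sequence relates to the GEE interaction test described earlier. The reader has to infer that the GEE interaction decides the BPI question.

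**Working it through.** **Step 1: the text side by side**

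| Analysis | Condition | Label in the visible text | Outcomes |
|---|---|---|---|
| GEE, 12-month time-by-treatment interaction | none | for testing hypotheses | continuous and categorical outcomes |
| Univariate active against placebo | none | exploratory | the outcomes, BPI not excluded |
| Adjusted longitudinal regression | only after a significant effect | hypothesis generating | same sequence |

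Whichever of the first two supplies the significant effect, the third exists only after significance. The selection therefore does not depend on how the paragraph is read. Its size does.

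**Step 2: inputs for an illustration**

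The plan gives 60 subjects (IV. Subject Selection) and two arms (VI. Study Procedures). The visible text gives no figure for alpha, effect, SD, allocation or dropout, so there is no figure of the plan's to reproduce. Assumed: 30 per arm, two-sided 0.05, true effect d = 0.5 SD, equal variances, correlation ρ = 0.5 between baseline and 12 months, complete data. The screening test is taken as the change-score contrast, which equals the interaction with complete data. The adjusted model is taken as adjustment for baseline BPI. The visible text names neither the univariate test nor the covariates.

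**Step 3: selection**

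- SE of the change contrast = √(2(1−ρ)) × √(2/30) = 1.000 × 0.2582 = 0.2582. Standardised effect k = 0.5/0.2582 = 1.936.
- P(significant) = Φ(1.936 − 1.960) + Φ(−1.936 − 1.960) ≈ 0.491 by the normal approximation, or 0.478 by the t distribution with 58 df. By the latter, no adjusted estimate is produced in about 52% of trials.
- Mean standardised error of the change contrast given significance = [φ(0.024) − φ(3.896)]/0.491 ≈ 0.812.
- SE of the adjusted estimate = √(1−ρ²) × √(2/30) = 0.866 × 0.2582 = 0.2236. Its correlation with the change contrast = √((1+ρ)/2) = 0.866.
- Mean adjusted estimate given significance = 0.5 + 0.866 × 0.2236 × 0.812 = 0.657, which is 0.657/0.5 = **1.31** times the truth. If the model is always run, the ratio is 1.00.

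Over d = 0.4 to 0.6 and ρ = 0.3 to 0.7, simulation with complete data gives ratios of 1.08 to 1.62. An adjusted model seen only when it is itself significant gives 1.07 to 1.64, so this is ordinary significance selection.

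Over the same range, the share of trials with no adjusted estimate depends on the screen and on missing data:

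| Change-score screen | Share with no adjusted estimate |
|---|---|
| Complete data, 30 per arm | 16–75% |
| Completers, 24 per arm (20% missing) | 25–79% |
| Completers, 18 per arm (40% missing) | 38–83% |

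**Step 4: using baseline BPI in the main model**

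At d = 0.5 and ρ = 0.5 with complete data, the standardised effect is 0.5/0.2236 = 2.236 with baseline adjustment, against 1.936 for the unadjusted change contrast. Power by the t distribution is about **59%** (57 df) against **48%** (58 df). Over the range in Step 3 the simulated gain is about 5 to 17 percentage points.

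**The case against.** The best defence is that the visible text points to a single confirmatory analysis by elimination. The GEE is there to test hypotheses, it names one contrast, BPI is the one primary endpoint, and the other routes are called exploratory or hypothesis generating. The adjective *similar* in the conditional sentence also presupposes the GEE as its reference. This stands, and it rules out three stronger readings that a reader might infer:

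- *That the p value deciding BPI is open.* The unconditional interaction test is the natural candidate. Aim 1 covers pain or itching, and the redacted text may settle the point. What is missing from the visible text is a label.
- *That the false-positive rate is inflated.* This would need an analysis labelled exploratory to be promoted to primary, and the larger inflation figures would also need a test of follow-up scores that the plan never mentions. If only the interaction test counts, the rate is nominal.
- *That no longitudinal BPI estimate exists without significance.* Only the adjusted regression is conditional. The GEE in the first paragraph gives an unselected estimate in every trial.

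The defence also says that the hypothesis-generating label and the caution about p values deal with the selection. They do so only in part. They warn about false positives, but they do not restore an estimate that was never computed or shrink one that was selected.

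Finally, the covariates are not visible, so the exaggeration is worked out for an assumed model. That limits the figures. It does not affect the direction of the bias.

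**Conclusion.** The concern holds in this form. By an explicit rule, adjusted longitudinal estimates appear only after a significant effect, with BPI not excluded, and so they are missing from non-significant trials and exaggerated on average in the rest. In the central illustration the ratio is 1.31, and it is 1.08 to 1.62 over the assumed range. These figures rest on the assumptions in the working and are not properties of the plan. No single share of trials without an adjusted estimate holds on every reading.

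Separately, the GEE interaction is the most natural confirmatory BPI analysis, but the visible text neither labels it so nor relates the later sequence to it. This is a clarification worth making, with medium confidence because of the redactions. It should be fixed, and fixing it is nearly free.

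**What to change.** 1. Delete the condition that a significant treatment effect must first be detected.
2. State that the 12-month time-by-treatment interaction from the longitudinal model is the primary analysis of BPI pain intensity, and that it is run whatever any univariate comparison shows.
3. Run the adjusted model unconditionally and report its estimates and confidence intervals in every case. Name its covariates in advance, unless the redacted text already does.
4. State which outcomes the univariate sequence covers, and that univariate and further adjusted analyses are supportive.
5. As an improvement rather than the repair of a contradiction, handle baseline BPI in the primary model by adjustment or a common baseline mean.

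The cost is SAP wording and a few extra model runs. No more patients or data are needed, because baseline outcomes are already collected.
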